10 DEVIATIONS FROM THE CLINICAL INVESTIGATION PLAN AND CLINICAL INVESTIGATION PLAN VIOLATIONS

The Investigator is not allowed to deviate from the CIP, except in an emergency.

10.1 Deviations

A deviation is a planned departure from the requirements of the CIP in order to deal with unforeseen circumstances.

Protocol Version 3.0, 24Oct2018

LINK Medical Research | Protocol template

Version 2.0 | Effective date 17Apr2018

Non-emergency Deviations:	In the event of a non-emergency deviation, prior approval by the Sponsor is required. If the deviation may affect the rights, safety, or welfare of participants or the scientific integrity of the clinical investigation, IEC approval is also required prior to implementation.
Emergency Deviations:	Emergency deviations required for the safety and welfare of the patient will be implemented by the Investigator and notified to the Sponsor as soon as possible after implementation.

The Sponsor is responsible for analyzing deviations and assessing their significance. Corrective action will be implemented to avoid repeated deviations, which may include suspending the clinical investigation and/or amending the CIP.

10.2 Clinical Investigation Plan Violations

Clinical Investigation Plan violations are deviations made without permission as a result of error or fraud/misconduct. Where the Monitor or Sponsor identifies that the Investigator is out of compliance, this will be notified to the Investigator in writing, with a request to correct the source of the deviation immediately. Corrective action will be implemented to avoid repeated non-compliance, which will usually include re-training and may include terminating the clinical investigation at the site.

10.3 Reporting of Deviations and Clinical Investigation Plan Violations

Depending on the nature of the deviation, they will either be recorded by the Investigator on the eCRF or documented by the Monitor and signed by the Investigator. Emergency deviations and violations which may affect the rights, safety or welfare of participants; or the scientific integrity of the clinical investigation will be notified to the IEC as soon as possible after the Sponsor has become aware of them.

11 SPECIAL REQUIREMENTS AND PROCEDURES

11.1 Good Clinical Practice

This clinical investigation will be conducted in accordance with Note for Guidance on Good Clinical Practice: CPMP/ICH/135/95, January 1997 (where applicable to medical devices) and the principles of the European Standard EN ISO 14155:2011 Clinical Investigation of Medical Devices for Human Patients – Good Clinical Practice.

11.2 Ethics

11.2.1 Institutional Ethics Review

The final CIP, including the final version of the patient information and consent form, must be approved or given a favorable opinion in writing by an IEC before enrollment of any patient into the investigation. The Investigator is responsible for informing the IEC of any amendment to the CIP as per local requirements.

11.2.2 Ethical Conduct of the Clinical Investigation

The clinical investigation will be conducted in compliance with applicable regulatory requirements and with the ethical principles of the latest revision of the Declaration of Helsinki as adopted by the World Medical Association ([Appendix 2](#)).

11.2.3 Patient Information and Consent

All patients will receive written and verbal information regarding the investigation prior to any investigation-related procedures. This information will emphasize that the participation in the investigation is voluntary and that the patient may withdraw from the investigation at any time and for any reason. All patients will be given the opportunity to ask questions about the investigation and will be given sufficient time to decide whether to participate in the investigation.

Before any clinical investigation-related procedures are undertaken, the ICF will be signed and dated by the patient (or their legally acceptable representative and/or witness, as applicable) and by the Investigator, or the qualified designee who gave the patient the verbal and written information.

If any data is transferred to EEA countries outside Sweden, the data will not identify any persons taking part in the clinical investigation in accordance with the EU General Data Protection Regulation (GDPR).

11.3 Patient Protection Procedures

11.3.1 Procedures in Case of Medical Emergency

The Investigator is responsible for ensuring that procedures and expertise are available to cope with medical emergencies during the clinical investigation.

11.3.2 Patient Data Protection

The written patient information explains that the data will be stored in a computer database, maintaining confidentiality in accordance with national data legislation, and that authorized representatives of the investigational site, Sponsor, RA, or an IEC require access to those parts of the medical records relevant to the clinical investigation, including medical history, for verification of data and appropriate conduct of the clinical investigation.

Confidentiality of patient data will be maintained at all times. Patient anonymity will be guaranteed and documentation relating to a patient will be kept in a secure location.

11.3.3 Insurance

The Sponsor has arranged the appropriate product liability and clinical trials insurance to cover the requirements of this clinical investigation.

11.4 Report and Publication

A final report of the investigation (a “Clinical Investigation Report” [CIR]) should be completed, even if the investigation is prematurely terminated. The report will be prepared by the Sponsor according to the guideline presented in Annex C of ISO 14155-1:2011(E).

All publications and presentations must be based upon the CIR.

Protocol Version 3.0, 24Oct2018

LINK Medical Research | Protocol template

Version 2.0 | Effective date 17Apr2018

All information supplied by the Sponsor in connection with this investigation will remain the sole property of the Sponsor and is to be considered confidential information. No confidential information will be disclosed to others without obtaining prior written consent from the Sponsor and will not be used except in the performance of this investigation.

The Investigator may publish results from this investigation; however as some of the information regarding the investigational medical device and development activities may be of a strictly confidential nature, the Sponsor must first be given the opportunity to review any publication manuscript prior to submission to journals, meetings or conferences.

The Sponsor may choose to publish or present data from this investigation. If an Investigator is offered first authorship, he/she will be asked to comment and approve the publication. The author order will be determined out of number of completed subjects. The Sponsor has the right to use the results for registration and internal presentation and for promotion.

11.5 Confidentiality

All processing of personal data will be stored confidential and handled according to legislations concerning the protection of personal data. Patients will be identified only by code. The informed consent form shall contain information about what personal data to be collected in the study and that this will be kept confidential. The provided information shall be sufficient to enable all subjects to give their consent not only to the participation in the study, but also to the processing of personal data. See also [Section 11.3.2](#).

12 CLINICAL INVESTIGATION TIME TABLE AND TERMINATION

Clinical investigation start (first patient first visit): 10 Nov 2018

Inclusion completed (last patient first visit): 10 Jan 2019

Last patient out (last patient last visit): February 2019

Appendix 1 Patient Questionnaire

Section 1. Vulvovaginal Symptoms

Day(s) 0, 4, 7, 14, and 35; or Day(s) 0, 4, 7, 11, 14, 21 and 42 if receiving prolonged treatment. Questions will be asked by the Investigator at Day(s) 0, 7, and 14 (for patients receiving prolonged treatment); and by the Clinical Trial Unit at remaining days.

Scoring of symptoms

	0 = none (absent)	1 = mild (slight)	2 = moderate (definitely present)	3 = severe (marked, intense)
Irritation				
Itching				
Burning				

The question “Have the symptoms returned, so that you need to seek medical care?” (yes/no) will be asked at Day(s) 14 and 35 if not receiving prolonged treatment and at Day(s) 21 and 42 if receiving prolonged treatment.

Section 2. Usability

Day 7 and Day 14 if receiving prolonged treatment:

Is the vaginal tablet easy to use?

- Yes
- No
- If no, provide reason: _____

Do you find the use of the vaginal tablet gentle?

- Yes
- No
- If no, provide reason: _____

Is the treatment odor free?

- Yes
- No

Is the treatment smear-free and dripless?

- Yes
- No

How do you generally regard the treatment?

1	2	3	4	5	6	7	8	9	10
Not satisfied					Very satisfied				

Section 3. Concomitant Medications

Day(s) 4, 7, 14, and 35; or Days(s) 4, 7, 11, 14, 21, and 42 if receiving prolonged treatment); patients will be asked: “since the last study visit or telephone contact, have you changed dose or taken any new medication?”

Section 4. Adverse Events

The following question will be asked at each patient contact: “since the last visit / telephone contact, have you had any health problems?”

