1 INTRODUCTION

1.1 Indication

Vaginal infection is a huge and today largely underestimated problem, affecting between 70% to 75% of women at some point in life, and between 5% to 8% of adult women have recurrent vulvovaginal candidiasis (VVC) with ≥ 4 episodes yearly.¹ As previously described, current antifungal agents for VVC treatment and prevention are prone to resistance development and many patients relapse after treatment.² Also, oral antifungal therapies are not recommended during pregnancy due to the potential risk of fetal harm and spontaneous abortions.^{3,4} Therefore, treatment guidelines recommend that topical, rather than oral, antifungal therapy is used in pregnant women.⁵

The vaginal microbiome is a dynamic system with a complex mixture of microorganisms in different ratios and quantities, which depend on lactic-acid producing bacteria to maintain a weakly acidic environment, see overview.⁶ Changes to vaginal microflora will increase the pH, thereby forming a favorable environment for vaginal pathogens. Vaginal or systemic antibiotics treatment is frequently followed by VVC, likely due to the elimination of the protective bacterial flora, thereby allowing *Candida* overgrowth.⁷⁻¹¹ Infections are also facilitated due to the mucosal effect of increased estrogen levels and a weakened immune system during pregnancy.¹² Recurrences are more common in pregnant women, and their therapeutic response is reduced compared to non-pregnant women.^{13,14} Further, contraceptive pills, menstruation, and diabetes mellitus have been identified as predisposing factors for VVC.^{15,16} *Candida albicans* is the most prevalent pathogen, which has been reported in epidemiological studies as represented in between 85% and 95% of vaginal isolations.¹⁷⁻¹⁹ *Candida glabrata* is the second most prevalent pathogen.²⁰

Many women diagnose themselves with VVC and purchase over-the-counter (OTC) antimycotics for treatment. However, many misdiagnose themselves, leading to unnecessary or inappropriate treatment;²¹ Ferris and colleagues found that only 34% of women who purchased OTC antimycotics for VVC did, in fact, have VVC.²²

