2.2 Secondary Objectives

To further investigate the clinical performance of the investigational product.

Secondary endpoints:

All patients

- Proportion of patients having a reduction in CVVS score on Day 7 compared to Day 0.
- Change in the CVVS score from Day 0 to Day 7.
- Proportion of patients having a reduction in the sum of the 3 vulvovaginal symptoms scores (itching, burning, and irritation) on Day 4 and Day 7, compared to Day 0.

- Change in the sum of the 3 vulvovaginal symptoms scores (itching, burning, and irritation) from Day 0 to Day 4 and Day 7.
- Usability, measured by patient questionnaire.

For patients not receiving prolonged treatment

- Recurrence rate on Day 14 and Day 35, defined as the proportion of patients clinically cured on Day 7 and thereafter responding “yes” to a yes/no question from the patient questionnaire on whether the symptoms have recurred.

For patients receiving prolonged treatment

- Proportion of patients receiving prolonged treatment.
- Clinical cure rate on Day 14, defined as the absence of signs and symptoms of VVC in terms of having a CVVS score equal to or below 3.
- Proportion of patients having a reduction in CVVS score on Day 14 compared to Day 0.
- Change in the CVVS score from Day 0 to Day 14.
- Proportion of patients having a reduction in the sum of the 3 vulvovaginal symptoms scores (itching, burning, and irritation) on Day 11, Day 14, Day 21, and Day 42, compared to Day 0.
- Change in the sum of the 3 vulvovaginal symptoms scores (itching, burning, and irritation) from Day 0 to Day 11, Day 14, Day 21, and Day 42.
- Recurrence rate on Day 21, and Day 42, defined as the proportion of patients clinically cured on Day 14 and thereafter responding “yes” to a yes/no question from the patient questionnaire on whether the symptoms have recurred.
- Proportion of patients receiving prescription for fluconazole on Day 14.

Exploratory endpoint variables:

All patients

- Effect on vaginal microbiome on Day 0 and Day 7.
- Vaginal pH on Day 7.

For patients not receiving prolonged treatment

- Effect on vaginal microbiome on Day 35.

For patients receiving prolonged treatment

- Effect on vaginal microbiome on Day 14 and Day 42.

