3.5.9 Day 14 (\pm 2 Days); Follow-up Telephone Contact

Applicable to patients NOT receiving prolonged treatment

Patients not receiving additional doses of investigational product on Day 7 will be contacted by the Clinical Trial Unit by telephone on Day 14. Patients will be asked questions from the patient questionnaire about VVC symptoms (itching, burning, or irritation), recurrence, concomitant medications, and AEs, if any.

Procedures performed:

- Vulvovaginal candidiasis recurrence
- Symptoms (itching, burning, or irritation) of VVC evaluated by patients according to the scoring scale
- Recording of:
 - concomitant medications, and
 - adverse events

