6.1.2 Patient Questionnaire

The questionnaire can be found in [Appendix 1](#).

The Clinical Trial Unit will call the patients on Day(s) 4, 14 and 35; or Day(s) 4, 11, 21, and 42 if receiving prolonged treatment; and ask questions from the patient questionnaire relating to vulvovaginal symptoms (itching, burning, or irritation), usability, concomitant medications, and AEs, if any.

Questions from *Section 1* in the patient questionnaire relating to vulvovaginal symptoms of itching, burning, and irritation will be asked to patients over telephone on Day(s) 4, 14, and 35; or Day(s) 4, 11, 21, and 42 if receiving prolonged treatment. A recurrence question will be asked to patients at Days(s) 14 and 35 if not receiving prolonged treatment and at Days(s) 21 and 42 if receiving prolonged treatment.

Questions from *Section 2* in the patient questionnaire relating to usability in will be asked to patients on Day 7, and Day 14 if receiving prolonged treatment.

Questions from *Section 3* and *Section 4* in the patient questionnaire relating to concomitant medications and AEs, respectively, will be asked to patients at each visit/telephone contact.

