#### B. For patients not receiving prolonged treatment

- vii] Recurrence rate on Day 14 and Day 35, defined as the proportion of patients clinically cured on Day 7 and thereafter responding "yes" to a yes/no question from the patient questionnaire on whether the symptoms have recurred

The endpoint vii] constitute binary variables.

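### Recurrence is defined as symptoms having recurred, but the only question asked also requires a need for medical care, so the reported rate is care-seeking recurrence

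*Protocol*

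**What the plan says.** Protocol 2.2 and 6.1 and SAP 3.2.1, 6.1, 7.9.2 and 8.8 describe recurrence in the same way. For patients without prolonged treatment, SAP 7.9.2 reads "Recurrence rate on Day 14 and Day 35, defined as the proportion of patients clinically cured on Day 7", followed by a yes "to a yes/no question from the patient questionnaire on whether the symptoms have recurred". For prolonged-treatment patients the cure visit is Day 14 and the question is asked on Days 21 and 42. None of these texts mentions medical care.

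Protocol 6.1.2 provides for one question: "A recurrence question will be asked to patients at Days(s) 14 and 35 if not receiving prolonged treatment", and on Days 21 and 42 otherwise. Appendix 1, Section 1 gives its wording: "Have the symptoms returned, so that you need to seek medical care", answered yes or no. It is the only recurrence item in the questionnaire.

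Symptoms are scored at the same contacts. Protocol 3.5.9 says of the Day 14 call: "Patients will be asked questions from the patient questionnaire about VVC symptoms (itching, burning, or irritation), recurrence, concomitant medications, and AEs, if any". Its procedure list includes "Symptoms (itching, burning, or irritation) of VVC evaluated by patients according to the scoring scale". Sections 3.5.11 to 3.5.13 repeat this for Days 21, 35 and 42.

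In SAP 7.9.2, the symptom-sum endpoints after Day 7 (xi and xii) cover prolonged-treatment patients only and compare with Day 0. For the other patients the later scores fall under the related variables, which are presented descriptively.

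**The concern.** The label and the instrument measure different things. The endpoint text describes a return of symptoms. The item asks for a return of symptoms and a need to seek care. A woman whose itching is back but who does not feel that she needs a doctor can truthfully say no, and she is then counted as free of recurrence. A reader of the results table would see a recurrence rate with nothing to show that it carries this second condition. The list of changes in SAP 7.11 does not mention it either.

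Recurrence is the only secondary performance endpoint after Day 7 for patients cured on the first course. The SAP regards it as important enough to create a second per-protocol set for it (7.2.2). Restricting the population does not change what the question measures.

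**Working it through.** The plan states no figure for this point, so there is none to reproduce. The check compares texts and then illustrates the sensitivity of the rate.

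**1. Definition against instrument.**

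| Source | Condition for recurrence |
|---|---|
| Protocol 2.2, 6.1; SAP 3.2.1, 6.1, 7.9.2, 8.8 | Cured at the reference visit, then yes to symptoms having recurred |
| Protocol Appendix 1, Section 1 | Symptoms returned, to the point of needing medical care |

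**2. Direction.** Let n be the number cured, R the number whose symptoms return, and m the number of those R who do not feel that they need care. If the item is answered as worded, the reported rate is (R - m)/n. This cannot exceed R/n and equals it only when m = 0.

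**3. Size, as an illustration only.** Inputs: 24 patients and a 70% cure rate (protocol 9.3), so n = 24 x 0.70 = 16.8, taken as 17. This assumes that all 24 are evaluable and followed up. R and m are assumed, because the documents give neither. One misclassified patient moves the rate by 1/17 = 5.9 points. Intervals are two-sided 95% Clopper-Pearson, the method in SAP 7.9.2. Suppose two patients answer yes:

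| m | Symptoms returned, R | R/n | 95% CI |
|---|---|---|---|
| 0 | 2 | 2/17 = 11.8% | 1.5% to 36.4% |
| 2 | 4 | 4/17 = 23.5% | 6.8% to 49.9% |
| 3 | 5 | 5/17 = 29.4% | 10.3% to 56.0% |

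Conversely, with R = 4 (23.5%), m = 1, 2 or 3 gives a reported 3/17 = 17.6%, 2/17 = 11.8% or 1/17 = 5.9%.

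**4. Whether the planned use of the scores fills the gap.**
- Prolonged treatment: SAP 8.7 counts a reduction when the change from Day 0 is below zero. Take a patient with symptom sums of 7 on Day 0, 1 on Day 14 and 5 on Day 42. Her change from Day 0 is 5 - 7 = -2, which counts as a reduction, although the sum has risen by 5 - 1 = 4 since the cure visit.
- No prolonged treatment: Day 14 and Day 35 scores are summarised by visit. A group summary does not compare each cured patient with her own Day 7 sum, so it does not classify who relapsed.

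**The case against.** The endpoint text points to the questionnaire, so the endpoint is not undefined. That stands: the fault is one of labelling and construct. Recurrence is secondary in a 24-patient feasibility study, with no hypothesis test on binary endpoints and no threshold to meet. That also stands and limits the consequence.

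Several stronger readings are tempting, but the documents do not support them.

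- *Persisting symptoms are also miscounted.* Returned and recurred both leave out a symptom that never went away, so endpoint and question do not differ here. That issue belongs to the cure threshold of CVVS 3 or below.
- *Self-treatment hides recurrences.* Protocol 1.1 does say "Many women diagnose themselves with VVC and purchase over-the-counter (OTC) antimycotics for treatment", but this describes women in general. Antifungals are prohibited during the study (5.7), and new medication is asked about at every follow-up contact, so use should be recorded. What is missing is a rule linking such use to recurrence.
- *The scores are discarded.* They are not. SAP 7.9 and 7.9.2 present them descriptively, and 7.1.1 plans individual listings. What is missing is a derived variable.
- *The rate is biased downward for candidal recurrence.* This is not established. Protocol 1.1 reports that only 34% of women buying over-the-counter antimycotics for VVC had it, and Table 2 schedules no microscopy or culture on Day 14 or 35. A need-for-care condition may screen out some non-candidal irritation. The understatement is clear only against any return of symptoms.
- *The illustrated rates are evidence of bias.* They are not. Each step is one patient, and the interval for 2/17 contains 5.9%, 11.8%, 17.6% and 23.5%.

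**Conclusion.** The mismatch is real and can be read directly from the texts. As planned, the trial would report care-seeking recurrence under the name of symptom recurrence, at Days 14 and 35 and at Days 21 and 42. The reported rate can be equal to or below the rate of any symptom return, provided that patients answer the item as worded. The size of the shortfall is unknown. The figure of 5.9 points per patient rests on the assumed 17 cured patients and shows only how sensitive a small denominator is. The planned descriptive summaries and the comparisons with Day 0 do not identify a rebound after cure. A reader might infer that the yes/no endpoint must be replaced; that is a trade-off, because care-seeking recurrence is a legitimate outcome when named as such. The primary endpoint is untouched. Correcting the label and adding a supportive analysis should be done.

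**What to change.** 1. In SAP 3.2.1, 7.9.2 and 8.8, call the existing result 'recurrence needing medical care', keep its derivation, and quote the item as asked. Section 8.8 names only Day 7 as the cure visit; it should also carry Day 14 for prolonged-treatment patients, as 7.9.2 does.

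2. Add a supportive, clearly labelled score-based analysis at the same contacts: the proportion of cured patients whose symptom sum rises above their own reference-visit sum (Day 7 or Day 14), with at least one symptom scored 2 or more as one stated cut-off. Report any recorded new antifungal use alongside it. This cut-off is a choice and is looser than the entry criterion, which needs at least two signs or symptoms at moderate level, plus discharge and positive microscopy.

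3. Fix the cut-off before the recurrence data are examined; otherwise label the analysis post hoc.

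4. Split the questionnaire item into return of symptoms and need for care only if follow-up is still open. Protocol section 12 planned the last visit for February 2019 and the SAP was finalised on 14 January 2020, so this is probably no longer possible.

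The cost is SAP wording and one derived variable from data already collected. The downsides should be stated in the report: the supportive rate may be higher, and it may include non-candidal symptoms because no microscopy or culture is scheduled at these calls.
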